## **8 OPTIONAL CORRELATIVE STUDIES**

### **8.1 Laboratory Correlative Studies**

#### **8.1.1 Circulating Biomarkers: Anti-fibrotic effects**

In pre-clinical and clinical studies circulating levels of collagen or profibrogenic molecules are used as surrogate biomarkers of the efficacy of RAS inhibition or other anti-fibrotic agents. We will determine how losartan affects plasma levels of ATII, collagen I and IV, and downstream mediators of ATII signaling [transforming growth factor  $\beta$ 1 (TGF $\beta$ 1), connective tissue growth factor (CTGF), thrombospondin-1 (TSP1), osteopontin] and profibrogenic cytokines [stromal derived factor-1 $\alpha$  (SDF-1 $\alpha$ ), interleukin (IL)-1 $\beta$ , IL-4, IL-10, and IL-13]. Granulocytes are a major source of TGF $\beta$  in PDAC. Therefore, we will measure how losartan affects the number of granulocytes in peripheral blood using flow cytometry and CBC. Because losartan modulates the levels of vascular endothelial growth factor (VEGF) and angiogenesis, we will also determine the circulating levels of angiogenic molecules. The changes in plasma biomarkers will be correlated with therapeutic response, outcome, tumor uptake of  $^{18}\text{F}$ -5FU and microvascular imaging parameters (see section 8.1.2).

Blood will be drawn by venipuncture, and the first 7-10 ml blood will be excluded or used for other analysis. The following 8 ml will be collected in an EDTA tube. The EDTA tube with the blood sample will be shipped in wet ice within 2 hours of drawing for further processing at Steele Laboratory at MGH.

Blood samples will be collected on Day 1, 8, 29 and 92. The day 29 and 92 blood draws may be completed +/- 3 days from their scheduled date. Blood can be drawn for this study at any time most convenient for the study participant.

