- (4) CT scans will be performed at least every 6 mo for the first 2 years and yearly for years 3-5. All follow up CT scans will be performed +/- 21 days of protocol-specified date
- (5) Restaging scans can be performed after pump disconnect during FOLFIRINOX cycles 4 and 8.

- (6) Blood for correlative studies will be obtained with clinical labs at pretreatment, day 8 of Cycle 1 FOLFIRINOX, at mid-FOLFIRINOX restaging, at post-FOLFIRINOX restaging, after chemo radiation therapy, 1 month after completion of capecitabine therapy, 1 month post-operatively (if surgery is performed), and within two weeks of radiographic progression (these blood draws are optional).
- (7) See section 8.2 for patient reported outcomes assessment timing.
- (8) Tumor measurements will be completed within +/-6 months of the scans. These measurements will be completed by the overall PI of the study.

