#### 10.1.2 Progression-free survival

Progression-free survival will be defined as the time from the start date of protocol therapy to first objective documentation of progressive disease (distant or local) or death. Patients who die without a reported prior progression will be considered to have progressed on the day of their death.

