### 14.3 Analysis of Secondary Endpoints

- 14.3.1 **Progression-free survival:** All patients who start induction chemotherapy will be analyzed based on the definition in Section 10.1.2. The progression-free survival duration of patients who are alive and progression will be censored at their date of last follow-up. The Kaplan-Meier method will be used to estimate progression-free survival with 90% confidence intervals constructed by Greenwood's formula.
- 14.3.2 **Overall survival:** Overall survival will be defined as the duration between the start date of protocol therapy and death. The survival time of patients who are not known to have died will be censored at the date they are last known to be alive. The Kaplan-Meier method will be used to estimate overall survival estimation with 90% confidence intervals constructed by Greenwood's formula.
- 14.3.3 **Toxicities:** All patients who begin induction chemotherapy will be included in the toxicity profile of Losartan combined with induction FOLFIRINOX. Summaries of toxicities will include the frequency and proportion of patients experiencing each toxicity, as well as summaries by toxicity category and toxicity grade. We shall report separately the additional treatment-related toxicity following radiation in patients who do not have progressive disease at the restaging interval after induction chemotherapy.
- 14.3.4 **Downstaging:** A fraction of patients may proceed to surgical resection following the conclusion of protocol therapy if the tumor shrinkage were sufficient to be considered resectable. The rate of downstaging to surgical resection will be determined as the proportion of initially unresectable patients who eventually undergo pancreaticoduodenectomy or distal pancreatectomy. The pathologic downstaging rate will be calculated as the proportion of resected patients with the primary tumor and nodes downstaged based on final pathology of the surgical specimen.
- 14.3.5 **Correlation of biomarkers with outcome:** Correlative studies will be conducted to characterize circulating collagen and angiogenesis biomarkers (8.1.1), as well as somatic genetic mutations characterized by the SNaPshot platform (8.1.2). Due to the modest patient numbers, analysis will be limited generally to two-group comparisons of each

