biomarker. Continuous values will be dichotomized at the median or a biologically meaningful threshold. The logrank test will be used to assess differences in progression-free survival and overall survival by biomarker status if at least 5 failure events have been observed within each subgroup. The correlative analysis will be purely exploratory due to the limited numbers expected per biomarker subgroup. In particular, analysis will be descriptive when the frequency of a genetic mutation is low.

14.3.6 ***Patient-reported outcomes***: We will use descriptive statistics to describe QOL (EORTC QLQ-C30), symptom burden (ESAS-r) and mood (HADS) for the entire study cohort. Mean values and standard deviations will be used to describe QOL and symptom burden (T-test or Wilcoxon as appropriate). We will score the HADS subscales for depressive and anxiety symptoms categorically, using a cut-off of >7 to describe the proportion of patients with these symptoms. We will use Chi-square or Fisher's Exact Test, as appropriate, to analyze the categorical variables.

14.3.7 ***Health care utilization***: We will use descriptive statistics to describe hospitalizations, ICU stays, ED visits and palliative care use for the entire study cohort. Mean values and standard deviations will be used to describe continuous variables (T-test and Wilcoxon rank sum, as appropriate). We will use Chi-square or Fisher's Exact Test, as appropriate, to analyze the categorical variables.

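### Cutting continuous plasma markers in two wastes information that a small exploratory analysis needs, on-treatment samples lack a time origin, and utilization means ignore unequal recording time

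*Combined protocol and SAP*

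**What the plan says.** **Circulating biomarkers (objective 1.3.8).** Section 14.3.5 sets the scope: "Due to the modest patient numbers, analysis will be limited generally to two-group comparisons of each" biomarker. It continues: "Continuous values will be dichotomized at the median or a biologically meaningful threshold". Groups are compared by logrank test for PFS and OS, provided each has at least 5 events. The section limits its own claims: "The correlative analysis will be purely exploratory due to the limited numbers expected per biomarker subgroup". No threshold is named for any analyte, and no significance level, effect size or event count is given.

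Section 8.1.1 shows that the markers are plasma concentrations sampled repeatedly: "Blood samples will be collected on Day 1, 8, 29 and 92". Note 6 to the study calendar adds that "these blood draws are optional".

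Both endpoints start at the beginning of treatment. For PFS, Section 10.1.2 says "Progression-free survival will be defined as the time from the start date of protocol therapy to first objective documentation" of progression, or death. For OS, Section 14.3.2 says "Overall survival will be defined as the duration between the start date of protocol therapy and death".

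**Health care utilization (objective 1.3.10).** Section 14.3.7 is descriptive: "Mean values and standard deviations will be used to describe continuous variables (T-test and Wilcoxon rank sum, as appropriate"). Section 8.3 has utilization recorded for the whole of the study. Section 5.6 says that after progression patients are followed for survival only. No rate, person-time denominator or fixed window appears.

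**The concern.** There are three separate issues.

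1. *Dichotomizing.* Modest numbers are a reason to spend few parameters. They are not a reason to discard the scale of a measurement, because a continuous Cox term and a two-group split each use one parameter. If risk changes steadily with the marker, the split discards information where events are fewest.

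2. *Time origin.* The plan does not distinguish a Day 1 value from a Day 8, 29 or 92 value. A patient must be alive and still attending to give a Day 92 sample. If such values define groups that are then compared from the start of therapy, patients are credited with time they had to survive in order to be sampled.

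3. *Utilization.* A mean count mixes the rate of use with the length of recording. A patient who dies or leaves early looks like a low user, which blurs the aim in Section 2.4 of understanding patients' experience of treatment.

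At stake is the precision and readability of secondary and exploratory results. No treatment decision or primary conclusion depends on them.

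**Working it through.** **The plan's own figures.** The only design figures are for the primary rule in Section 14 (at least 9 R0 resections in 50). Exact binomial calculation gives a type I error of 0.0579 at 10% (stated 6%) and power of 0.9084 at 25% (stated 91%). Both reproduce, and neither bears on this point. The figures below rest on assumptions.

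**Information kept by a split.** Assume the marker is normal on the analysis scale and the log hazard is linear in it. A cut at quantile q, with normal deviate c, has efficiency phi(c)^2 / [q(1 − q)]. At the median this is (1/(2 pi)) / 0.25 = 2/pi = 0.637, a loss of 36.3%. Cuts at the 60th, 70th, 80th and 90th percentiles keep 0.622, 0.576, 0.490 and 0.342. Shape matters: a uniform marker loses 25% at the median. If the effect is linear on a raw lognormal scale, the loss is 48% (sigma 0.5) to 73% (sigma 1).

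**Power.** Assume D = 40 events and a two-sided 5% test. Power is Phi(ln(HR) × sqrt(D × efficiency) − 1.96), with efficiency 1 for the continuous term and 0.637 for the split.

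| HR per SD | ln(HR) × sqrt(40) | Continuous | × sqrt(0.637) | Median split |
|---|---|---|---|---|
| 1.3 | 1.659 | 38% | 1.324 | 26% |
| 1.5 | 2.564 | 73% | 2.046 | 53% |
| 2.0 | 4.384 | 99% | 3.498 | 94% |

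Simulation with 50 patients and about 40 events gives 35% vs 25%, 67% vs 47% (69% vs 49% in a second run) and 98% vs 87%. The gap is therefore not an artefact of the large-sample formula. With 30 events, HR 1.3 gives 30% vs 21% and HR 1.5 gives 60% vs 43%.

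**Choice of cut.** Suppose, hypothetically, that the better of the median and one other cut were reported. Under the null, the two test statistics have correlation sqrt((1 − q)/q), which is 0.816, 0.707 and 0.577 for a second cut at the 60th, 67th and 75th percentile. The chance that either exceeds 1.96 in absolute value is 7.7%, 8.3% and 8.8%. Simulation with the 67th percentile gives 8.9% (40 events) and 9.5% (30 events), against 5.4% and 5.6% for the median alone. A nominal 5% becomes about 8–9%.

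**What a landmark costs.** Assume exponential PFS. Day 92 is 92/30.44 = 3.02 months. The share with an event by then is 1 − exp(−ln 2 × 3.02 / median), which is 21%, 16% and 11% for assumed medians of 9, 12 and 18 months.

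**Utilization.** Assume 0.1 admissions per month for everyone. Six months of recording gives 0.1 × 6 = 0.6 expected admissions, and 24 months gives 0.1 × 24 = 2.4. The counts differ fourfold although the rate of use is the same. Pooled over the two patients, 3.0 admissions in 30 months recovers 0.1 per month.

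**The case against.** The strongest reply is that this is a preference about an analysis the plan already calls exploratory, with a floor of 5 events per group and wording that restricts it only generally to two groups. Sections 8.1.1 and 8.1.2.1 also speak of correlating markers with outcome, so a continuous analysis is not barred. That stands as to weight. It does not remove the point, because the sentence on continuous values is a plain commitment to cut them, and no continuous-scale survival model is specified.

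It is also fair that the stated reason attaches to two-group comparisons, and might mean only that multivariable models are ruled out. The sentence on dichotomizing gives no reason of its own. Either way, small numbers do not support the cut.

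The power figures depend on assumed hazard ratios, events and significance level. At HR 1.3 both methods are weak, and the continuous term does not rescue the screen. Optional draws could leave fewer than 40 events among sampled patients.

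Mean admissions per patient is a legitimate description of total burden in a single-arm cohort. That stands, so the rate should be added beside the mean.

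Two stronger readings are tempting and not supported:

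- *That the threshold will be picked after outcomes are seen.* The plan does not say so; it only leaves the choice open.
- *That Section 5.7 contradicts Section 5.5 by both removing and retaining patients who progress.* Section 5.7 gives a general rule and then an explicit exception for progression, which agrees with Section 5.6. The open question is only whether utilization recording under Section 8.3 continues past progression.

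**Conclusion.** The point holds as a modest improvement to secondary and exploratory analyses. For a roughly normal marker with a log-linear effect, a median split keeps about 64% of the information. At an assumed 40 events this costs about 12 points of power at HR 1.3 per SD, 19 at 1.5 and 5 at 2.0 by formula. The documents give no marker shape, effect size, event count or significance level, so these sizes are illustrative.

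The missing distinction between baseline and on-treatment samples is a gap in the text: as written, a later value could be used to group patients from time zero. Mutations (objective 1.3.7) are already binary, so the loss from cutting does not apply to them.

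For utilization, means without recorded time cannot separate low use from short observation, and the end of recording needs to be stated.

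A reader might infer that the trial's efficacy conclusion is weakened. It is not: the 9-of-50 rule uses none of these analyses.

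**What to change.** **Section 14.3.5, still exploratory.**
- As the main analysis of baseline markers, fit a Cox model for PFS and for OS with the marker continuous on the log scale. Report the hazard ratio per SD or per doubling with a 90% confidence interval, the level already used in Sections 14.3.1 and 14.3.2.
- Keep the median split for Kaplan-Meier display, and the logrank test for mutations.
- For on-treatment values or changes, start the clock at a landmark set at the sampling time and include only patients still event-free then.
- Name any biological threshold and its source before outcomes are analysed.

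**Section 14.3.7.** Report events per patient-month over the time utilization was actually recorded, alongside the per-patient summaries. First reconcile Section 8.3 with Section 5.6, so that it is clear whether recording extends past progression.

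**Cost.** SAP wording, a little analysis time, and one recorded end date of utilization collection per patient. Treatment, visits, sample size and the primary analysis are unchanged.

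**Downsides.** The Cox term assumes log-linearity. If the true effect is a step at the median, the continuous term is the one with about 64% efficiency, so check residual plots and show the split beside it. A landmark discards early events. None of this addresses the number of analytes in Section 8.1.1, so the results remain exploratory.

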### **1.3 Secondary Objectives**

- 1.3.1 To determine the progression-free survival of patients with locally advanced disease who receive FOLFIRINOX-Losartan and radiation therapy.
- 1.3.2 To determine overall survival in patients treated with FOLFIRINOX-Losartan and radiation therapy.
- 1.3.3 To determine the overall survival of patients with locally advanced disease who receive FOLFIRINOX-Losartan without radiation (i.e. patients who demonstrate progression at restaging.)
- 1.3.4 To determine the toxicity of FOLFIRINOX – Losartan in patients with locally advanced pancreatic cancer.
- 1.3.5 To determine the toxicity of FOLFIRINOX – Losartan and radiation in patients with locally advanced pancreatic cancer.

- 1.3.6 To determine the rate of downstaging to surgical resection of FOLFIRINOX-Losartan followed by radiation in patients with locally advanced pancreatic cancer.
- 1.3.7 To determine the correlation between a panel of somatic genetic mutations (SNaPSHOT) and outcome in locally advanced pancreatic cancer treated with FOLFIRINOX-Losartan +/- radiation/capecitabine.
- 1.3.8 To determine the correlation between circulating biomarkers of TGF- $\beta$ 1 downregulation, including circulating Collagen I levels, and outcome in locally advanced pancreatic cancer treated with FOLFIRINOX-Losartan +/- radiation/capecitabine.
- 1.3.9 To describe quality of life, symptom burden and mood in the study population.
- 1.3.10 To measure utilization of health services (emergency room, hospital and intensive care unit, palliative care) in the study population.

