A randomized trial comparing the efficacy of gemcitabine and FOLFIRINOX in metastatic pancreatic cancer also assessed QOL, using the European Organization for the Research and Treatment of Cancer QOL Questionnaire C30 (EORTC QLQ-C30).[31] The authors demonstrated that FOLFIRINOX not only prolonged survival, but also significantly reduced QOL impairment compared to gemcitabine for patients with metastatic cancer. Thus, in addition to the utility of describing the symptom burden and QOL in patients with locally advanced pancreatic cancer, it will also be useful to compare these outcomes in patients receiving different chemotherapy regimens.

We will use the EORTC QLQ-C30, a validated instrument designed for prospective clinical trials that evaluates five functions (physical, role, cognitive, emotional, and social), and nine symptoms (fatigue, pain, nausea and vomiting, dyspnea, loss of appetite, insomnia, constipation, diarrhea, and financial difficulties) to measure QOL.[39] We will use the Edmonton Symptom Assessment System-revised (ESAS-r) to measure symptoms, which has been previously validated in patients with advanced cancer.[40] The ESAS-r consists of ten items assessing pain, fatigue, drowsiness, nausea, anorexia, dyspnea, depression, anxiety, well-being, and a free-response item. We will include constipation as the free-response item. The ten items are scored on a scale of 0-10 (0 reflecting no reported presence of the symptom and 10 reflecting the worst possible severity of the symptom). We will instruct patients that items are to be rated based on the previous 24-hour period. We will use the Hospital Anxiety and Depression Scale (HADS) to assess symptoms of depression and anxiety.[41] The HADS is a 14-item questionnaire that contains two 7-item subscales assessing depression and anxiety symptoms during the past week. The questionnaire consists of a four-point item response format that quantifies the degree to which participants experience a particular emotion. Scores on each subscale range from 0 to 21, with a cutoff of 8 or greater denoting clinically significant depression or anxiety symptoms.

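### HADS is summarised only as the proportion scoring above 7 while the companion scales keep means and SDs; adding the full 0-21 score would sharpen the description of mood at almost no cost

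*Combined protocol and SAP*

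**What the plan says.** Objective 1.3.9 is "To describe quality of life, symptom burden and mood in the study population". Section 14.3.6 opens in the same spirit: "We will use descriptive statistics to describe QOL (EORTC QLQ-C30), symptom burden (ESAS-r) and mood (HADS) for the entire study cohort". It then treats the three instruments differently.

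- QLQ-C30 and ESAS-r: "Mean values and standard deviations will be used to describe QOL and symptom burden", with a t-test or Wilcoxon test mentioned.
- HADS: "We will score the HADS subscales for depressive and anxiety symptoms categorically, using a cut-off of >7", to give the proportion of patients with symptoms.
- Tests for categorical variables: "We will use Chi-square or Fisher's Exact Test, as appropriate, to analyze the categorical variables".

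Section 2.3 explains the cut: "Scores on each subscale range from 0 to 21, with a cutoff of 8 or greater denoting clinically significant depression or anxiety symptoms". On whole-number scores, above 7 and 8 or greater are the same rule, so the two sections agree.

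Section 8.2.1 schedules all three instruments together: at consent, at weeks 3, 7, 11 and 15 of chemotherapy, in week 2 of chemoradiotherapy, and in follow-up. No comparison, time point, effect size or power is given for any patient-reported outcome.

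**The concern.** HADS is the instrument chosen for mood, one of the three parts of objective 1.3.9, and it is the only one of the three reduced to yes or no. The documents give no reason. Section 2.3 presents 8 as a level that marks clinically significant symptoms, not as the only permitted summary.

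On the planned summary, a patient who moves from 8 to 18 has not changed, and one who moves from 7 to 8 has changed fully. A patient already above 7 at consent cannot register worsening on HADS at all. With an accrual goal of 50, and fewer patients at later visits, throwing away the score also costs precision. What is at stake is how well the trial can describe anxiety and depression through treatment. The R0 decision rule does not depend on it.

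**Working it through.** **Figures in the plan.** The only operating characteristics stated are for the primary rule (at least 9 R0 resections in 50). Exact binomial gives P(X ≥ 9) = 0.058 at a 10% rate and 0.908 at 25%, which reproduces the stated 6% and 91%. For HADS there is no figure to reproduce.

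**Inputs from the documents.** Range 0-21, cut above 7, 50 patients. For a later visit I also use 35 pairs. In the retrospective series of chemotherapy followed by chemoradiation in section 2.2.1, 29.3% had metastatic disease after three months, and 50 × (1 − 0.293) ≈ 35.

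**Assumed inputs, none in the documents.** SD 4; pre/post correlation ρ of 0.4 to 0.6; baseline mean 5 to 7; mean worsening 1 to 2 points (0.25 to 0.50 SD); two-sided 5%. SD is held at 4, but what matters most is the shift relative to the SD. A 1.5-point shift with SD 3 to 5 is 0.50 to 0.30 SD, inside the range covered.

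**One case by formula** (baseline mean 6, shift 1.5, ρ = 0.6, 50 pairs).

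- Full score: SD of change = 4 × √(2 × (1 − 0.6)) = 3.58. Noncentrality = 1.5 / (3.58/√50) = 2.96. Power of the paired t-test ≈ 83%.
- Cut, with 7.5 as the boundary: 35.4% are above it before, 50.0% after and 27.1% both times. So 22.9% move up and 8.3% move down. The difference is 0.146. Its standard error is √(0.311/50) = 0.0789 under no change and √((0.311 − 0.146²)/50) = 0.0761 under this shift. Power of McNemar's test ≈ Φ((0.146 − 1.96 × 0.0789)/0.0761) ≈ 46%.

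**Simulation** (20,000 trials per cell; scores rounded and clipped to 0-21, which slightly shrinks the realised shift; paired t-test against uncorrected McNemar, so that only the cut differs). Ranges are over baseline means 5, 6 and 7.

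| Pairs | Shift | ρ | Full score | Above-7 cut | Relative loss |
|---|---|---|---|---|---|
| 50 | 1.0 | 0.4 | 34% | 19-21% | 38-44% |
| 50 | 1.0 | 0.6 | 47-48% | 21-24% | 50-55% |
| 50 | 1.5 | 0.4 | 64-65% | 37-41% | 37-42% |
| 50 | 1.5 | 0.6 | 80-82% | 43-47% | 42-47% |
| 50 | 2.0 | 0.4 | 87-88% | 59-63% | 28-32% |
| 50 | 2.0 | 0.6 | 96-97% | 68-71% | 27-29% |
| 35 | 1.0 | 0.4 | 25-26% | 13-15% | 43-48% |
| 35 | 1.0 | 0.6 | 34-36% | 15-17% | 54-57% |
| 35 | 1.5 | 0.4 | 49-50% | 26-28% | 44-48% |
| 35 | 1.5 | 0.6 | 65-67% | 30-32% | 51-54% |
| 35 | 2.0 | 0.4 | 73-74% | 43-46% | 38-41% |
| 35 | 2.0 | 0.6 | 88-89% | 50-52% | 41-43% |

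**Cross-check on information kept.** For independent groups, the share of information kept by a cut with prevalence p is φ(c)²/(p(1 − p)), where c is the standardised cut. At p = 0.5 this is 0.1592/0.25 = 64%; at p = 0.2 it is 49%. For paired change it is 52% at p = 0.5 with ρ = 0.4, and 43% with ρ = 0.6.

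**The tests actually named.** Chi-square and Fisher's test treat visits on the same patients as independent. Applied to pre/post data (35 pairs, 1.5 points, ρ = 0.6, baseline mean 5 to 7.5), chi-square has about 16-18% power. Part of that shortfall comes from ignoring the pairing, so it is not counted in the table.

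**The case against.** The strongest reply is that no test of mood change is planned. The objective and section 14.3.6 are both descriptive, chi-square and Fisher's test are tied to no comparison, and the pre/post test above is supplied by this review. The cut is fixed in advance and matches the clinical threshold in section 2.3, and a prevalence is a legitimate descriptive summary. All of this stands. It means that no stated power claim is broken, and that the proportion should be kept. It does not answer the descriptive loss: one proportion is a thin summary of a 0-21 score, whether or not anything is tested.

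Three stronger readings are tempting, and the documents do not support them.

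- A reader might infer that most of the power is lost. Like for like, the loss is about 27-57% over the assumed range. It passes half only at the higher correlations with a 1-point shift, or with 1.5 points in 35 pairs. Measured as information for paired change, the loss passes half more readily (ρ around 0.5 or more), but that depends on a correlation the documents do not give.
- A reader might infer that a real shift will usually be missed. A 2-point shift in 50 pairs with ρ = 0.6 is still detected 68-71% of the time on the cut.
- A reader might infer that worsening among patients already above the cut goes unseen altogether. That is true of HADS alone. ESAS-r has depression and anxiety items, and QLQ-C30 has an emotional function scale. Both are given at the same visits and summarised by mean and SD.

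**Conclusion.** The point holds as a minor improvement to a secondary, descriptive endpoint. Section 14.3.6 plans HADS only as a proportion above 7, which hides changes that stay on one side of the cut. For a pre/post comparison in 35 to 50 patients, that would give up roughly a quarter to a half of the power. The percentages rest wholly on the assumed SD, correlation, baseline mean and shift; the direction does not. No decision rule, sample size or safety rule is affected.

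**What to change.** In section 14.3.6, replace the HADS sentence with text such as: *Each HADS subscale (0-21) will be summarised at each assessment by mean, SD and median. Within-patient change from the pre-treatment score will be reported with a confidence interval. The proportion of patients scoring above 7 will also be reported as a clinical summary. If change is tested, a paired or repeated-measures method will be used.*

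The cost is one sentence and one extra table. The HADS form in the appendices already carries separate anxiety and depression totals, so no new data are needed, and the planned proportion is kept.
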